### 9.4. Benefit-Risk Assessment

Benefit-risk of rivaroxaban in the setting of COVID-19 will be explored.

## 10. SUBJECT COMPLETION / WITHDRAWAL

### 10.1. Completion

The total duration of the study for a subject who completes the study after randomization is 60 days. All feasible efforts and measures will be made to collect complete vital status and other outcome data from randomization to the EOT/EOS visit for each subject randomized in this study regardless of compliance with study drug or visits. For subjects who are lost to follow-up or withdraw consent from the study, efforts will be made to obtain their vital status and other outcomes from permitted sources.

It is important to note that withdrawal of consent does not withdraw permission to collect vital status and other outcomes. Withdrawal of permission to collect vital status and other outcomes must be made separately. In cases where subjects indicate they do not want to "continue", investigators must

determine whether this refers to discontinuation of study treatment (the most common expected scenario), unwillingness to attend follow-up visits, unwillingness to have telephone contact, unwillingness to have any contact with study personnel, or unwillingness to allow contact with a third party (e.g., family member, doctor). In all cases, every effort must be made to continue to follow the subject, and vital status and other outcomes must be determined for all randomized subjects.

## **10.2. Discontinuation of Study Treatment**

If a subject's study treatment must be discontinued before the end of the treatment or thromboprophylaxis phase, the subject must continue to be followed for efficacy and safety endpoint. During the study, should the subject develop any condition, which in the investigator's judgment requires long-term therapeutic anticoagulation, or fibrinolysis, the subject will have the study drug either temporarily interrupted or permanently discontinued and will be managed as deemed appropriate by the treating physician. The subject will be asked to continue in the study to be followed for efficacy as well as safety endpoint.

### **10.2.1. Temporary Interruption of Study Treatment**

If the subject requires (re)-hospitalization (hospitalization is defined as a combined total of inpatient and/or emergency room stay  $\geq 24$  hours) during the study drug treatment for reasons other than the primary efficacy endpoints or bleeding, the subject should be maintained on the study drug or SOC treatment at the discretion of the investigator. If the treating physician feels that the subject requires any anticoagulation or another anticoagulation during the re-hospitalization, study drug needs to be temporarily interrupted, but can be resumed upon hospital discharge and stop of any prohibited medication.

In addition, the study drug should be temporarily interrupted if the subject:

- Develops any medical condition that may require use of anticoagulant therapy, thromboprophylaxis, fibrinolysis or poses an increased bleeding risk.
- Undergoes percutaneous coronary intervention, coronary artery bypass graft, any other interventional procedure, that may require use of anticoagulant therapy, thromboprophylaxis, or poses an increased bleeding risk.
- For temporary interruption of study drug for an elective procedure or surgery, it is suggested that investigators follow measures in Table 1 and Table 2 (Section 10.2.2 Approach to Subjects with Temporary Interruption of Study Treatment).
- Experiences a major bleeding event other than intracranial bleeding. For less severe bleeding events, investigator discretion is allowed. If possible, study drug should be resumed when the bleeding event has resolved, and the cause has been identified and corrected.
- If a subject develops a new neurologic deficit or significant alteration in mental status suggesting a cerebral vascular accident. Once a diagnosis is definitively made and appropriate treatment is provided, the study drug may be restarted at the discretion of the investigator.
- Develops a platelet count less than 50,000/ $\mu\text{l}$ . If a repeat platelet count is obtained, and the result indicates that the abnormal platelet count was spurious, study drug may be restarted. If the finding was not spurious, study drug may be restarted after 2 consecutive values greater than 75,000/ $\mu\text{l}$  apart have been obtained.
- Has a serious adverse event that is considered by the investigator to be possibly related to or exacerbated by study drug administration.
- Requires a prohibited therapy on a temporary basis (see Section 8, Prestudy and Concomitant Therapy).

### **10.2.2. Approach to Subjects with Temporary Interruption of Study Treatment**

The clinical condition of patients with moderate to severe COVID-19 may deteriorate during the hospital stay and the subject may need supportive care on an ICU. In critical cases in need of mechanical ventilation, shock or organ failure requiring ICU care, rivaroxaban treatment will be switched to full dose anticoagulation with LMWH or UFH if treating physicians consider the bleeding risk not as very high. In case the bleeding risk is considered higher the patients would be switched to prophylactic anticoagulation.

If the patient's condition improves during the course of the disease, the treating physician should restart rivaroxaban at the earliest possible time point judged as safe. However, it is also possible to discontinue and stop the treatment with rivaroxaban, if there are safety concerns at the discretion of the treating physician. If the study drug is temporarily interrupted to allow a procedure to be performed, the routine measures described in Table 1 and Table 2 should be considered:

**Table 1: Preoperative Interruption of Rivaroxaban: A Suggested Management Approach (adapted from Spyropoulos and Douketis 2012)**

Patient Renal Function	Low Bleeding Risk Surgery (2-3 drug half-lives between last dose and surgery) a	High Bleeding Risk Surgery (4-5 drug half-lives between last dose and surgery) b
Normal or mild impairment (CrCl ≥50 mL/min), or moderate (CrCl ≥30 and <50 mL/min) impairment	Last dose : 2 days before surgery (skip 1 dose)	Last dose : 3 days before surgery (skip 2 doses)

CrCl, creatinine clearance.

a aiming for mild-to-moderate residual anticoagulant effect at surgery (<12-25%).

b aiming for no or minimal residual anticoagulant effect (<3-6%) at surgery.

**Table 2: Postoperative Resumption of Rivaroxaban: A Suggested Management Approach**

Low Bleeding Risk Surgery	High Bleeding Risk Surgery
resume on evening of or day after surgery (within 24 hours postoperative)	resume 2 to 3 days after surgery (within 48 to 72 hours postoperative)

### 10.2.3. Permanent Discontinuation of Study Treatment

If a subject must be permanently discontinued from study drug before the end of the thromboprophylaxis phase, this will not result in automatic withdrawal of the subject from the study, and the subject should continue to be followed for efficacy and safety outcomes (for details see Section 3.1).

A subject should be permanently discontinued from study drug if:

- The investigator believes that for safety reasons (i.e., adverse event) it is in the best interest of the subject to stop study drug.
- The subject develops any condition which requires anticoagulation or thromboprophylaxis extending beyond the treatment phase of the study (e.g., atrial fibrillation, VTE).
- The subject becomes pregnant.
- The subject has a fall in eGFR to below 20 mL/min/1.73m^2 or 2 consecutive measurements less than 30 mL/min/1.73m^2 at least 1 week apart (as calculated by the CKD-EPI formula) during the study.
- The subject requires hemofiltration or dialysis on a permanent basis
- The subject requests to discontinue study drug permanently
- The subject has a hemorrhagic stroke, or intracranial bleeding

If the subject permanently discontinues study drug before Day 35 post randomization, he/she should be instructed to complete an unscheduled visit and the remaining scheduled visits (if not yet completed).

The eCRF is to be completed to identify the reason for permanent discontinuation of study drug. The investigator will provide a narrative to describe any adverse event that occur up to the 35-day post randomization visit. The appropriate adverse event or serious adverse event sections of the eCRF are to be completed. If study drug is terminated for a serious adverse event, expedited reporting (within 24 hours) is also required as outlined in Section 12.3.2, Serious Adverse Events.

### 10.3. Withdrawal from the Study

A subject will be withdrawn from the study for any of the following reasons:

- Lost to follow-up (only after all means of all subsequent contact, including locator services where permitted by law, up until the day 60 post randomization, have been exhausted, lost to follow-up will be declared).
- Withdrawal of consent (unless specifically refused by the subject, subject contact will be made to obtain vital status and other outcomes until the day 60 post randomization visit).
- If during the study the subject loses his ability to consent (eg intubation). In this case, after the subject recovers his/her ability to consent, he/she will be asked again to consent and continue participating actively in the trial.

If a subject is lost to follow-up, every reasonable effort must be made by the study site personnel to contact the subject and determine the reason for discontinuation/withdrawal. The measures taken to follow up must be documented.

Study drug assigned to the withdrawn subject may not be assigned to another subject. Subjects who withdraw will not be replaced.

If a subject withdraws consent from study or is lost to follow-up, his or her vital status and other outcomes will be collected at day 35 post randomization either by telephone or in person, or if applicable, by a review of the subject's medical or public records unless this contact is not allowed by local regulations.

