### 11.1 Definition of populations included in the analyses

The primary efficacy analysis as well as all secondary efficacy analyses will be based on the full analysis set (FAS) following the intention-to-treat principle and will include all randomized patients. Safety analyses will be based on the safety set (SAF) including all randomized patients with at least one dose of study medication or at least one dose of SOC (UFH or LMWH).

For time-to-event endpoints, study discontinuations will be dealt with as independent right censoring. Patients discontinuing study drug will be follow up for endpoints. Otherwise missing values will be dealt with using multiple imputation methods. If, against expectations, the proportion of patients with premature study discontinuations is substantial, shared random effects models simultaneously modelling time to primary outcome and time to study discontinuation will be used to explore the robustness of the treatment effect.

Sensitivity analyses will be performed in all patients (a) completing at least 7 days of treatment and (b) completing the study adherent to the study protocol. These will be referred to as the (a) while on treatment population and (b) per-protocol (PP) population.

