	
 
• New myocardial infarction (MI)
 
• Non-hemorrhagic stroke
 
• All-cause death
 
• Progression to intubation and invasive ventilation
   
• <del>Development of DIC</del>
 
• <del>Seven-category ordinal scale recommended by the WHO as clinical improvement scale for patients with respiratory infections (23-25)</del>
 
• <del>Number of days requiring invasive ventilation</del>
 
• <del>Number of days requiring non-invasive ventilation</del>
 
	
loss of ability to consent only if the patient agreed to be re-consented. Therefore many data needed for these secondary endpoints couldn't be adequately documented.

9.2.1. Efficacy Evaluations, Outcomes and Adjudication
 
Other endpoints of interest
	
Other endpoints of interest:
 
 
• Length of hospital stay
 
• Time to intubation
 
• Re-hospitalization due to heart failure
 
• Re-hospitalization due to any other reason
 
• <del>Proportion of patients requiring catecholamines, time to catecholamines and time on catecholamines</del>
 
• Effects on coagulation parameters for thrombosis (TAT, PAI-1, PF-4, TF, TF-activity)
 
• Effects on inflammatory and fibrotic coagulation parameters for thrombin formation (D-dimer interleukines, interferons, growth factors)
 
• Change of N-terminal prohormone brain natriuretic peptide (NT-pro-BNP)
 
• Unscheduled outpatient visits
 
	
The endpoint "proportion of patients requiring catecholamines" was deleted due to the fact that patients during their time of ICU were not allowed to be documented only in case of a re-consenting after regaining the ability to give consent. Therefore, the information on catecholamine application couldn't be captured adequately.
 
The measurement of markers for thrombosis, inflammation, fibrosis and growth was added as "other endpoints on interest" for those patients who gave the consent for this substudy. The aim is to characterize both treatment groups in regard of the different markers and to understand the course of the disease under the different treatment conditions.

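### Withdrawal for loss of capacity (for example at intubation) is driven by the outcome, but Section 11.1 has no rule for it and its only check for informative dropout no longer fits the primary endpoints

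*Protocol*

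**What the plan says.** Section 10.3 (Withdrawal from the Study) gives three grounds for withdrawal. The third begins: "If during the study the subject loses his ability to consent (eg intubation". The way back is that "after the subject recovers his/her ability to consent, he/she will be asked again to consent and continue participating actively in the trial". The last paragraph of the section arranges outcome retrieval at day 35 for two groups only: "If a subject withdraws consent from study or is lost to follow-up, his or her vital status and other outcomes will be collected". Loss of capacity is not among them. Section 10.1 says, without exception, that "vital status and other outcomes must be determined for all randomized subjects".

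Section 11.1 puts all randomized patients in the full analysis set and states two rules: "For time-to-event endpoints, study discontinuations will be dealt with as independent right censoring", and "Otherwise missing values will be dealt with using multiple imputation methods". Neither makes an exception for intubation or for death after withdrawal. If discontinuation turns out unexpectedly frequent, "shared random effects models simultaneously modelling time to primary outcome and time to study discontinuation will be used" to examine robustness.

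Section 11.2 names the primary endpoints: D-dimer and the seven-category scale, both at day 7. In Attachment 2, category 6 is invasive ventilation on ICU and category 7 is death. In Section 11.3, intubation is a component of the secondary composite.

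The table of changes in Section 18.1.1 explains why the DIC and ventilation-day endpoints were dropped. Observation could go on in case of "loss of ability to consent only if the patient agreed to be re-consented", so data for those endpoints were poorly documented.

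**The concern.** Withdrawal under this rule follows from getting worse. Intubation is the protocol's own example, it equals category 6 of the co-primary scale, and it can come before death. Only patients who recover can consent again, so those who die after intubation are the least likely to come back into the data.

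Independent censoring and a general imputation rule both suit dropout that is unrelated to the unseen outcome, given what was observed. Here the relation is built into the rule. The amendment removed endpoints because of this loss, and then made co-primary a scale whose two worst categories depend on the same patients.

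Two things are at stake: a distorted between-arm comparison at day 7, and missed deaths, thromboembolic events and bleeding after intubation.

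**Working it through.** **Inputs from the protocol (Section 11.7, Section 18.1.1).** Two-sided alpha 0.05; 40 per group; log D-dimer difference 0.44, SD 0.8, correlation 0.5; relative effect 0.68 on the ordinal scale; about 100 recruited for 80 evaluable; 111 randomized.

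**Assumed, because the protocol gives no figure.** The share of each arm lost to ventilation before the day-7 visit (window -2/+1 days), written qC for control and qT for rivaroxaban; a D-dimer value g log units higher in those patients, with g from 0.7 to 1.4 (about 2- to 4-fold); imputed values that resemble those of observed patients in the same arm.

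**Step 1: the plan's own sample size.** The ANCOVA SD is 0.8 × √(1 − 0.5²) = 0.693. Then n = 2 × (1.960 + 0.842)² × 0.693² / 0.44² = 38.9, so 39 per arm. With 40 per arm, power is 81.1% (normal) or 80.1% (t). For the ordinal scale, Noether's formula gives N = (1.960 + 0.842)² / (12 × 0.25 × 0.18²) = 80.7 in total, and power with 80 is 79.6%. Also 80 / (1 − 0.20) = 100. The sample size reproduces and is not at issue.

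**Step 2: co-primary scale.** Let p be the relative effect among patients not ventilated. With ventilated patients scored 6 and the others in categories 1 to 5,

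p1 = (1 − qC)(1 − qT) p + (1 − qT) qC + 0.5 qC qT.

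Imputation that resembles observed patients returns p instead. For 15% v 5% and p = 0.5: 0.95 × 0.85 × 0.5 + 0.95 × 0.15 + 0.5 × 0.05 × 0.15 = 0.404 + 0.1425 + 0.004 = 0.550.

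| Lost, control v rivaroxaban | p (imputed) | p1 (ventilated kept at 6) |
|---|---|---|
| 15% v 5% | 0.500 | 0.550 |
| 10% v 5% | 0.500 | 0.525 |
| 5% v 10% | 0.500 | 0.475 |
| 10% v 20% | 0.500 | 0.450 |
| 10% v 10% | 0.500 | 0.500 |
| 20% v 10% | 0.564 | 0.596 |
| 10% v 20% | 0.564 | 0.496 |
| 10% v 10% | 0.564 | 0.552 |

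The value 0.564 comes from an assumed control distribution of 15/25/20/30/10% over categories 1 to 5 and an odds ratio of 1.5 in favour of rivaroxaban. A shift of 0.05 is 0.05 / 0.18 = 28% of the distance from 0.5 to the design value of 0.68.

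**Step 3: D-dimer.** If loss does not depend on baseline and the effect among the others is −0.44, keeping the ventilated patients gives −0.44 + g(qT − qC), while imputation stays near −0.44.

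- 20% v 10%: −0.51 to −0.58, a reduction of 40% to 44%.
- 10% v 20%: −0.37 to −0.30, a reduction of 31% to 26%.
- Equal loss: −0.44.

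The shift of 0.07 to 0.14 is 16% to 32% of the target difference.

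**Step 4: time-to-event endpoints.** In the composite, intubation is itself the event, so the patient has counted before being withdrawn. Death, VTE, MI and stroke are also analysed separately. There the same patient is censored at withdrawal as if no sicker than those still followed. Bleeding after withdrawal is likewise unseen. Section 11.5 does treat premature study discontinuation as a competing event when estimating bleeding probability, so the independence assumption bears there on the Cox hazard ratio. Patients who lose capacity without intubation are also exposed in the composite.

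**Step 5: the stated check.** The shared random effects model in Section 11.1 joins dropout to a time to primary outcome. Section 11.2 has a D-dimer value and an ordinal score at a fixed day. The model cannot be run on either.

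**The case against.** The protocol does not specify the imputation model. It leaves detail to the statistical analysis plan, which could use intubation status, and nothing obliges anyone to impute a category 6 that is known. Death is not a ground for withdrawal, and an observed death is simply category 7. Section 10.1 asks for vital status on everyone. Sections 9.1.3 and 15.2.3 allow contact with a legal representative when a patient cannot attend. Patients needing immediate ICU care are excluded and outpatients are eligible, so early intubation may be uncommon: in 111 patients split evenly, 15% v 5% is about 8 v 3. The study calls itself explorative.

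Most of this stands, and it limits the point. A reader might infer that the worst outcomes are removed from both primary analyses. The documents do not support that. Independent censoring is confined to time-to-event endpoints, and neither primary endpoint is one. Imputation keeps patients in the full analysis set and replaces their values. Only loss before the day-7 visit matters there. A reader might also see a contradiction with the note in Section 4.2, but that note concerns patients whose eligibility changes before randomization.

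Three things are not answered. The independence assumption is stated, not left open. The stated check cannot be applied to the current primary endpoints. The broad retrieval provisions conflict with Section 10.3 and with the sponsor's own account that these patients could not be followed. That account concerns the deleted secondary endpoints, however, and does not say how many day-7 values were lost.

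**Conclusion.** The point holds in a limited form and should be fixed. The protocol withdraws patients for a reason tied to the outcome, contradicts itself on whether their outcomes are collected, and applies censoring and imputation rules that ignore the reason.

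Bias in the primary comparisons is conditional. It needs loss before day 7 that differs between arms, and imputed values that resemble those observed. Under the assumed rates it reaches 0.05 on the relative effect (up to 0.07 if there is also an effect among the other patients) and 0.07 to 0.14 log units for D-dimer. It can hide a benefit or a harm. With equal loss it is zero for D-dimer and at most about 0.01 for the relative effect. Unequal loss cannot be ruled out in advance, because the secondary hypothesis is that rivaroxaban reduces a composite that includes intubation.

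In the time-to-event analyses the harm falls on death, VTE, MI, stroke and bleeding after intubation, and little on the composite.

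**What to change.** - **Sections 10.1 and 10.3:** reconcile them on which outcomes may be collected after loss of capacity, and from which permitted sources.
- **Section 11.2, ordinal scale:** at day 7, score known invasive ventilation as 6 and known death as 7 instead of imputing them.
- **Section 11.1, censoring:** do not assume independence for this withdrawal reason. Use permitted vital status for the analysis of death, and report death or intubation as a sensitivity analysis. Merely relabelling the withdrawal as a competing event would leave a cause-specific Cox hazard ratio unchanged.
- **Section 11.1, D-dimer:** include known intubation or ICU status in the imputation. A last D-dimer or last score adds little, because the Time and Events Schedule has no assessment of either between baseline and day 7.
- **Section 11.1, sensitivity:** replace the shared random effects model with a delta-adjusted or tipping-point analysis for these patients.

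The cost is protocol and analysis-plan wording and some programming. No further recruitment is planned and none is needed. The drawback is that a patient extubated before day 7 may be scored slightly too badly.

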## 11. STATISTICAL METHODS

This is an explorative study and hence analyses have an explorative nature. In the following we describe the principles for the planned analyses. Further details will be documented in a statistical analysis plan (SAP).

### 11.1 Definition of populations included in the analyses

The primary efficacy analysis as well as all secondary efficacy analyses will be based on the full analysis set (FAS) following the intention-to-treat principle and will include all randomized patients. Safety analyses will be based on the safety set (SAF) including all randomized patients with at least one dose of study medication or at least one dose of SOC (UFH or LMWH).

For time-to-event endpoints, study discontinuations will be dealt with as independent right censoring. Patients discontinuing study drug will be follow up for endpoints. Otherwise missing values will be dealt with using multiple imputation methods. If, against expectations, the proportion of patients with premature study discontinuations is substantial, shared random effects models simultaneously modelling time to primary outcome and time to study discontinuation will be used to explore the robustness of the treatment effect.

Sensitivity analyses will be performed in all patients (a) completing at least 7 days of treatment and (b) completing the study adherent to the study protocol. These will be referred to as the (a) while on treatment population and (b) per-protocol (PP) population.

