### **Early Permanent Study Drug Discontinuation/Early Withdrawal from Study**

If the subject permanently discontinues study drug before day 35 post randomization, he/she should be instructed to complete the scheduled visits.

Because the primary efficacy analysis of the study is based upon the ITT principle, the investigator should inform the subject of the importance of returning for all study visits. It is imperative for the integrity of the trial and results to have vital status and outcomes ascertainment. If the subject is unwilling or unable to return for any visits, the site should collect as much follow-up information as possible, including contacting the subject or legally acceptable representative by telephone or by mail to determine vital status and if an outcome has occurred, as agreed to by the subject during the initial informed consent process. If applicable, vital status and other outcomes should be obtained by reviewing the subject's

medical or public records unless this contact is not allowed by local regulations. If the subject withdraws consent from the study, this must be documented in the source document and the subject will be asked to supplement the withdrawal of consent with a signed written statement documenting refusal for all subsequent contact.

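### The censoring rule for time-to-event endpoints, on its plain wording, leaves out deaths and events that the protocol requires sites to retrieve after consent withdrawal

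*Protocol*

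**What the plan says.** **The analysis rule.** Section 11.1 bases all efficacy analyses on the "full analysis set (FAS) following the intention-to-treat principle and will include all randomized patients". It then states: "For time-to-event endpoints, study discontinuations will be dealt with as independent right censoring". The next sentence covers a different group: "Patients discontinuing study drug will be follow up for endpoints". The Synopsis carries the same rule. Section 11.1 also plans a joint model of time to primary outcome and time to study discontinuation, to be used if premature discontinuations are substantial.

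**The bleeding analysis.** Section 11.5 and the Synopsis (Safety Endpoints) list premature study discontinuation beside death as a competing event in the Aalen-Johansen estimate.

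**The collection duty.**
- Section 9.1.3, on early drug discontinuation and early withdrawal, invokes the ITT principle and adds: "It is imperative for the integrity of the trial and results to have vital status and outcomes ascertainment".
- Section 10.1 notes that "withdrawal of consent does not withdraw permission to collect vital status and other outcomes". For those lost or withdrawn, "efforts will be made to obtain their vital status and other outcomes from permitted sources", and it closes with "vital status and other outcomes must be determined for all randomized subjects".
- Section 10.3 says that for a patient who withdraws consent or is lost, "his or her vital status and other outcomes will be collected at day 35 post randomization", by contact or from records where regulations allow. It declares loss to follow-up only after contact attempts up to day 60 are exhausted.

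**The concern.** The efficacy composite and the bleeding outcomes are defined up to day 35, which is when Section 10.3 has outcomes collected for patients who have withdrawn. The retrieval is therefore timed for these analyses and justified by the ITT principle. If study discontinuation is itself the censoring time, a patient who withdraws consent on day 10 and is found in records to have died on day 20 enters the Cox model as event-free and censored on day 10.

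The endpoints at stake are the composite, all-cause death, the other single components, and bleeding. With 111 patients randomized (Section 18, rationale for the sample size change), events will be few. Leaving out known ones costs information, and it makes the result rest on an independence assumption that is not needed where status is known.

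**Working it through.** No figure in the protocol depends on the censoring rule, so there is none to reproduce. The check has two parts.

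**1. Does the wording make discontinuation the end of observation?**
- Section 11.1 separates stopping drug (followed up) from study discontinuation (censored). Patients withdrawn under Section 10.3 fall into the second group.
- The joint model uses time to study discontinuation, so discontinuation is a dated event.
- Section 11.5 makes it a competing event, and a competing event ends observation when it occurs. A bleed retrieved later is then not counted, and the estimated probability of bleeding is lowered even if leaving is unrelated to prognosis.
- No sentence gives the censoring date or says that a retrieved outcome overrides it.

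The plain reading is that retrieved outcomes stay out. A reading in which they count is possible, but it is not written down.

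**2. How much could be lost?**

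The protocol gives no event rate, withdrawal rate or retrieval rate for these endpoints. Assumed inputs:
- 35-day composite risk of 15% without extra risk after leaving
- 10% of patients leaving, uniformly over days 1-20
- hazard after leaving multiplied by k = 1, 2 or 4
- full retrieval

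Daily hazard: λ = −ln(0.85)/35 = 0.00464.

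Probability of an event after leaving on day L, up to day 35: 0.10 × exp(−λL) × [1 − exp(−kλ(35 − L))].

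At the mean leaving day, L = 10.5, exp(−λL) = 0.952. The table uses this day; averaging over days 1-20 changes the share lost by less than 0.1 percentage point.

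| k | Probability of an event after leaving | True 35-day risk | Share of events lost | Events lost among 111 |
|---|---|---|---|---|
| 1 | 0.10 × 0.952 × 0.108 = 0.0102 | 15.0% | 0.0102/0.150 = 6.8% | 1.1 |
| 2 | 0.10 × 0.952 × 0.203 = 0.0194 | 15.0 − 1.02 + 1.94 = 15.9% | 0.0194/0.159 = 12.2% | 2.2 |
| 4 | 0.10 × 0.952 × 0.366 = 0.0348 | 15.0 − 1.02 + 3.48 = 17.5% | 0.0348/0.175 = 19.9% | 3.9 |

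A simulation of 400,000 event times gave 6.8%, 12.2% and 19.7%, with true risks of 15.0%, 15.9% and 17.4%. Kaplan-Meier with censoring at leaving gave about 15% in all three cases. With an unchanged hazard the rule costs events but does not bias the risk. With k = 2 or 4 it understates the risk by about 0.9 or 2.4 percentage points.

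**Effect on the hazard ratio.** If leaving and its link to prognosis are the same in both arms, the hazard ratio is roughly unchanged. If patients with raised risk leave only the control arm and the arms are otherwise equal, the ratio of true 35-day cumulative hazards is ln(0.85)/ln(1 − 0.159) = 0.94 for k = 2 and ln(0.85)/ln(1 − 0.174) = 0.85 for k = 4. Censoring at leaving would show about 1.0. The direction reverses if they leave only the rivaroxaban arm.

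**The case against.** The strongest reply is that the protocol nowhere says retrieved events are discarded. The censoring sentence sits in a paragraph on missing data, followed by multiple imputation for values otherwise missing. Sections 9.1.3 and 10.1 tie ascertainment to ITT, and Section 9.2.1 says adjudicated results feed the final analyses. On that view censoring applies only where information ends, and the exact date belongs in the SAP. Part of this stands: a reader might infer an explicit instruction to throw known deaths away, and the text does not support that. Nor is the ITT population breached, since the full analysis set still holds every randomized patient. The conflict concerns follow-up. But the protocol states a rule, and its dated-event and competing-event language points away from the harmless reading.

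Three further limits stand in full.
- Loss to follow-up is declared only after day 60, past the endpoint window, so that route adds little.
- A reader might infer that open-label leaving which differs by arm makes censoring informative. It does not do so by itself, because treatment is in the Cox model. Leaving must relate to prognosis beyond the modelled covariates.
- The gap in Section 11.7 between about 100 recruited and 80 evaluable patients concerns the day-7 endpoints and cannot serve as a withdrawal rate.

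The joint model and the sensitivity analyses planned in Section 11.3 are some protection. The joint model, however, is conditional on substantial discontinuation and refers to time to primary outcome, although the primary endpoint is now day-7 D-dimer.

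**Conclusion.** The point holds as a conflict between a stated censoring rule and a stated collection duty. On plain wording, outcomes retrieved after consent withdrawal are left out of the time-to-event analyses. It mainly concerns patients who withdraw consent without refusing outcome collection.

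Its size is unknown. The figures of 7% of events lost with an unchanged hazard, and 12-20% with a hazard two to four times higher, rest wholly on the assumed 10% leaving on days 1-20, 15% risk and full retrieval. In 111 patients that is about one to four events. The hazard ratio is distorted only if leaving is related to prognosis beyond the modelled covariates, most clearly when the share of events lost for that reason differs between arms.

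The day-7 D-dimer and ordinal-scale analyses and the sample size are unaffected. The change is worth making, but it is no threat to the primary result of a trial that calls its analyses explorative.

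**What to change.** Replace the censoring sentence in Section 11.1 and the Synopsis with wording to this effect: patients are censored at the last date on which their status for the endpoint concerned is known, up to day 35; events and event-free status obtained after study discontinuation from permitted sources both count; study discontinuation is the censoring time only where no later information exists or its collection was refused.

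Align the bleeding text in Section 11.5 and the Synopsis, so that premature study discontinuation does not act as a competing event where later status is known. Keep censoring at discontinuation as a sensitivity analysis, and carry the rule into the SAP.

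The cost is a few sentences and no new data collection, since Sections 10.1 and 10.3 already require the data. There is one drawback. Deaths are easier to find in records than proof that a patient had no VTE or MI, so retrieval may favour events over event-free status. For that reason both must be treated alike, and completeness of retrieval should be reported by arm and endpoint.
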